10.2 Analysis Sets, Subgroups, and Covariates

10.2.1 Analysis Sets

Full Analysis Set: The full analysis set (FAS) includes all randomized subjects who received at least 1 dose of investigational product.

10.2.2 Covariates

Baseline covariates will include, but are not limited to the following:

- Age
- Sex
- Baseline LDL-C

Approved

10.2.3 Subgroups

Subgroup analysis of the primary endpoint will be conducted for, but not limited to the following variables:

- Age (< median, ≥ median; < 65 years of age, ≥ 65 years of age)
- Sex
- Baseline LDL-C (< median, ≥ median)

10.2.4 Handling of Missing and Incomplete Data

Subjects may be missing specific data points for various reasons. In general, data may be missing due to a subject's early withdrawal from study, a missed visit, or non-evaluability of a data point or endpoint at a particular time. The frequency and pattern of missing data for efficacy endpoints will be assessed through descriptive summaries of the measurements over time. The reason of missing the final OCT measurement will be tabulated. For subjects with missing post-baseline FCT, the missing primary endpoint will be imputed using multiple imputation (see [Section 10.3.2.2](#)).

10.3 Statistical Analyses

The statistical analysis plan will be developed and finalized before database lock. Below is a summary of the timing and methods for the planned statistical analyses. To preserve study integrity, the final analysis will be conducted and reported following the EOS, as defined in [Section 5.3.1](#).

10.3.1 Planned Analyses

10.3.1.1 Final Analysis

There will be no interim analysis for this study. The final analysis will be conducted after all subjects have either completed all the scheduled study visits or have early terminated from the study. At that time, the database will be cleaned, processed, locked, and a snapshot will be taken; the study will also be unblinded. Based on the snapshot, efficacy and safety analyses will be performed.

10.3.2 Methods of Analyses

10.3.2.1 General Considerations

Summary statistics for continuous variables will include the number of subjects, mean, median, SD or standard error, minimum, and maximum. For categorical variables, the frequency and percentage will be given.

Statistical inferences will be provided for analyses of primary and secondary efficacy endpoints. Unless specified otherwise, all statistical tests are 2-sided with a significance

level of 0.05; no statistical inference and imputation will be conducted for analyses of safety of exploratory endpoints.

Multiplicity Adjustment Method

In order to preserve the family wise type 1 error rate at 0.05 for testing the primary and secondary endpoints, the primary analysis of primary endpoint will be tested first. If the treatment effect from the primary analysis of the primary endpoint is significant at a significance level of 0.05, the secondary endpoints will be tested with significance level of 0.05 using the Hochberg method

10.3.2.2 Efficacy Analyses

Endpoint	Statistical Analysis Methods
Primary	The primary analysis method of the primary endpoint is to use the analysis of covariance (ANCOVA) model, including terms for treatment group, stratification factor (current statin use [> 4 weeks or ≤ 4 weeks] at randomization), and baseline FCT as covariates. Least square means and corresponding 95% confidence intervals will be calculated for each treatment group and for the difference between the treatment groups. For subjects with missing post-baseline FCT, the missing primary endpoint will be imputed using multiple imputation (details provided in SAP). FAS will be used. A sensitivity analysis of the primary endpoint will be conducted using nonparametric method and FAS.
Secondary	ANCOVA model including terms for treatment group, stratification factor (current statin use [> 4 weeks or ≤ 4 weeks] at randomization), and respective baseline value as covariates.
Exploratory	Will be described in the statistical analysis plan finalized before database lock

10.3.2.3 Safety Analyses

10.3.2.3.1 Adverse Events

Subject incidence of all treatment-emergent adverse events will be tabulated by system organ class and preferred term. Tables of fatal adverse events, serious adverse events, adverse events leading to withdrawal from investigational product or other protocol-required therapies, and significant treatment-emergent adverse events will also be provided. Subject incidence of device-related events, if applicable, will be tabulated by system organ class and preferred term.

10.3.2.3.2 Laboratory Test Results

The analyses of safety laboratory endpoints will include summary statistics at each scheduled visit for each treatment group. Shifts in grades of safety laboratory values between the worst on-study value from baseline to the EOS will be tabulated for each treatment group.

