12.2 Appendix 2. Clinical Laboratory Tests

The tests detailed in [Table 12-1](#) will be performed by the local laboratory, or the central laboratory.

Whenever the local laboratory is used to make either a study treatment decision or response evaluation, the results must be entered into the case report form (CRF).

Protocol-specific requirements for inclusion or exclusion of subjects are detailed in [Section 6.1](#) to [Section 6.2](#) of the protocol.

Additional tests may be performed at any time during the study as determined necessary by the investigator or required by local regulations.

Table 12-1. Analyte Listing

Laboratory: Chemistry	Laboratory: Coagulation	Laboratory: Hematology	Other Labs
Creatinine hs-Troponin (I/T)	-	-	Serum or Urine Pregnancy Lipid Testing 
 • Total cholesterol • HDL-C • LDL-C • Triglycerides • VLDL-C • Non-HDL-C • ApoA1 • ApoB • ApoB/ApoA1 ratio • Total Cholesterol/HDL-C ratio • Lp(a) Biomarkers

Apo = apolipoprotein; HDL-C = high-density lipoprotein cholesterol; hs = high sensitive; LDL-C = low-density lipoprotein cholesterol; Lp(a) = lipoprotein(a); VLDL-C = very low-density lipoprotein cholesterol

Laboratory/analyte results that could unblind the study will not be reported to investigative sites or other blinded personnel until the study has been unblinded. Central laboratory results of the lipid testing will be blinded post-treatment until unblinding of the clinical database and will not be reported to the investigator post-screening. In addition, investigators and staff involved with this trial and all medical staff involved in the subject's medical care should refrain from obtaining lipid panels between randomization and at least 12 weeks after the subject ends the study (to avoid potential unblinding).

Approved

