5.3 Demographics and Baseline Related Definitions

Age

Age is the subject's age in years at enrollment as recorded on the eCRF.

Baseline Lipid and Lipid-related Parameters

Baseline values for LDL-C, triglycerides and troponin are defined as the concentrations measured through **local lab at screening**. **Baseline values for other lipids (eg, total cholesterol, HDL-C and VLDL-C), ApoA1, ApoB, Lp(a) and their derived parameters (eg, ratio between them) are defined as the concentrations measured through central lab on Study Day 1.**

Baseline Laboratory Variables

Baseline values for laboratory variables are defined as the assessment measured at screening.

Baseline Concomitant Medication Usage and Medical History

Baseline values for background statin therapy, lipid-modifying concomitant medication usage and medical history are defined as the assessment measured at screening. For concomitant medication that is not lipid-modifying baseline is defined as measurement at study day 1.

Baseline Image Data

Baseline values for OCT, IVUS image data are defined as the assessment measured at screening.

Baseline Vital Signs

Baseline values for vital signs are defined as the last non-missing value collected prior to or on Study Day 1.

Change (absolute change) from Baseline

The arithmetic difference between a post-baseline value and baseline for a given time point:

Change (absolute change) from baseline = (post-baseline value – baseline value).

Percent Change from Baseline

The percent change from baseline for a given variable at a given time point is defined as:

$100 \times [(value \text{ at given time point} - baseline \text{ value}) / baseline \text{ value}]$.

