9.6.2 Laboratory Test Results

Descriptive statistics will be provided for actual values and changes from baseline in selected laboratory parameters at each protocol-specified scheduled visit. Laboratory analytes are provided in the protocol (Appendix 2).

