9.6.5 Exposure to Concomitant Medication

The number and proportion of subjects receiving medications of interest (MOI) will be summarized by preferred term or category for each treatment group as coded by the World Health Organization Drug (WHODRUG) dictionary. **Statin intensity will be summarized by treatment group at each targeted scheduled visit date.**

10. Changes From Protocol-specified Analyses

There are no changes to the protocol-specified analyses.

11. Literature Citations / References

12. Appendices

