Appendix B. Common Terminology Criteria for AEs (CTCAE)

Refer to the NCI Common Terminology Criteria for Adverse Events (CTCAE) for adverse event grading and information. The CTCAE is available at the following link: <http://evs.nci.nih.gov/ftp1/CTCAE/About.html>

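### Does SAP Section 10 need rewriting because the laboratory grade-shift table and some other protocol safety outputs are missing from SAP 9.6?

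*Protocol*

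**What the plan says.** Protocol 10.3.2.3.2 makes two promises for safety laboratory data: summary statistics by scheduled visit and arm, and a shift table, "Shifts in grades of safety laboratory values between the worst on-study value from baseline to the EOS will be tabulated for each treatment group".

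On the data side, Table 2-1 marks chemistry in the screening column alone. The chemistry column of Table 12-1 (Protocol Appendix 2) reads "Creatinine hs-Troponin (I/T", and the coagulation and hematology columns hold only a dash. The same appendix allows discretionary testing: "Additional tests may be performed at any time during the study as determined necessary by the investigator".

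In the SAP, Section 5.3 says "Baseline values for laboratory variables are defined as the assessment measured at screening". Section 9.6.2 plans descriptive statistics for actual values and "changes from baseline in selected laboratory parameters at each protocol-specified scheduled visit", with no shift table. The only grading reference is Appendix B, which points to the CTCAE "for adverse event grading and information".

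Three other places matter:

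- **Adverse events.** Protocol 10.3.2.3.1 says tables of "adverse events leading to withdrawal from investigational product or other protocol-required therapies, and significant treatment-emergent adverse events will also be provided". SAP 9.6.1 covers withdrawal from investigational product, has no table labelled as significant events, and adds summaries of injection-site reactions and of hypersensitivity or allergic reactions.
- **Physical measurements.** Protocol 10.3.2.3.4 plans summaries of these. SAP 9.6 has no matching section.
- **Exposure.** Protocol 10.3.2.3.5 lists patient-months, dose categories and total quantity used. SAP 9.6.4 plans a general exposure summary.

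SAP Section 10 then states: "There are no changes to the protocol-specified analyses".

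**The concern.** Two things look wrong. First, the protocol promises a table that its own visit schedule cannot fill. A shift needs a baseline and at least one later value, and for chemistry the only scheduled draw is the baseline. Second, the SAP drops that table and trims other protocol outputs, while the section meant to record such departures says there are none.

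What would be at stake is the reading of the safety report. Someone relying on SAP Section 10 would expect every protocol safety table. On finding no post-baseline chemistry, that reader might take the gap for a clean laboratory profile.

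**Working it through.** No power or error-rate figure is involved. The check is a count of scheduled data and a comparison of the two lists of outputs.

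**Scheduled data (Protocol Table 2-1, Table 12-1)**

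- Visit columns: screening, day 1, weeks 4, 12, 24, 36, 50 and 52 = 8.
- Columns with chemistry: 1 (screening). Chemistry draws after the first dose: 0.
- Chemistry pairs per subject = 0, so 150 × 0 = 0 for the planned sample.
- Fasting lipids: day 1, week 24 and week 50 = 3 draws, 2 of them after baseline. Change from baseline under SAP 9.6.2 is therefore feasible for lipids. Lipid changes are in any case an exploratory endpoint, analysed under SAP 9.5.3.
- Other scheduled laboratory work after the first dose: pregnancy tests (weeks 24 and 50) and biomarker samples (week 50).

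The first half of the concern is therefore right for scheduled chemistry.

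**Protocol 10.3.2.3 against SAP 9.6**

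The protocol has 6 safety subsections and SAP 9.6 has 5; physical measurements is the one without a counterpart. By output:

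| Protocol output | SAP 9.6 | Status |
|---|---|---|
| Laboratory grade shifts | none | absent |
| Physical measurements | none | absent |
| Significant treatment-emergent events | no table of that name; injection-site and hypersensitivity summaries added | unclear |
| Events leading to withdrawal from investigational product or other required therapies | investigational product only | narrowed |
| Exposure: months, dose categories, quantity | general summary | narrowed |
| Treatment-emergent, fatal, serious and device-related events; laboratory summary; vital signs; concomitant medication | present | matched |

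The count depends on the rule:

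- Clearly absent: 2.
- Adding the unclear item: 2 + 1 = 3.
- Adding both narrowed items as well: 3 + 2 = 5.

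A count of 4 requires the narrowed withdrawal table to be included and the narrowed exposure summary to be left out, and no single rule does that. The two firm items are enough to make the Section 10 sentence inaccurate.

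**Does any result depend on the missing items?**

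- *Grade shifts.* With no scheduled post-baseline chemistry, following the protocol to the letter would give an empty table, or one built from tests ordered case by case.
- *Physical measurements.* Protocol 9.2.1.5 describes height and weight, but neither has a row in Table 2-1, so there is no series of visits to summarise. Baseline values can go in the tables of SAP 9.4, whose list is open-ended.
- *Withdrawal and exposure.* The events leading to withdrawal from background therapy remain in the overall adverse-event tables, and SAP 5.4 defines exposure in months. What is lost is detail.
- *Inference.* Under SAP 9.1, safety endpoints carry no statistical inference. The safety endpoint in Protocol 4.1 is the incidence of treatment-emergent and serious adverse events, which SAP 9.6.1 covers in full.

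**The case for a change.** The best case for a change is that Section 10 exists to declare departures, that its statement is untrue, and that putting it right would take a few sentences and no data. Background statin is required of every subject (Protocol 7.1.4), so a table of withdrawals from other required therapies would not be empty by design. Discretionary tests do not rescue the shift table as a comparison between arms, because they are ordered selectively.

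The inaccuracy stands, and so does the point about selective testing. Three things limit the rest.

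- A corrected list is harder to write than it looks. Declaring that no table of significant events is planned could itself be untrue if the injection-site and hypersensitivity summaries serve that purpose. A list that omitted the exposure summary would still be incomplete.
- The fear that missing chemistry would be read as absence of findings is conjecture. Table 2-1 shows that none was scheduled, Protocol 9.2.4 sends clinically relevant laboratory changes to the Event CRF, and SAP 9.6.2 is confined to selected parameters at scheduled visits.
- The protocol's shift sentence speaks of on-study values and is not confined to scheduled visits, so unscheduled results could be tabulated. Such a table would be sparse and hard to interpret, but not strictly impossible.

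A related matter lies outside the analysis plan. In Protocol Appendix 7, the permanent-discontinuation column of Table 12-2 and the two-fold limb of the close-observation trigger refer to a pre-drug AST/ALT value. Table 12-1 lists neither enzyme and Table 2-1 schedules neither. Those passages must be reconciled by the sponsor's clinical team. The layout of Table 12-2 was read from a PDF, and the point bears on no planned analysis.

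**Conclusion.** The facts behind the concern are correct, but no change to the plan follows. Protocol 10.3.2.3.2 promises a table with 0 scheduled chemistry pairs behind it, and SAP 9.6 sensibly omits it. The no-changes sentence in SAP Section 10 is a clerical inaccuracy covering 2 firm omissions and up to 3 further items that are narrowed or unclear. With the SAP followed exactly, the primary and secondary analyses, type I error, power and the adverse-event safety endpoint are all unaffected. A corrected declaration would improve traceability and change no number or conclusion.

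This rests on three assumptions: that safety laboratory values in the protocol means the chemistry analytes of Table 12-1, a term the protocol leaves undefined; that Table 2-1 was extracted correctly in showing chemistry at screening only; and that investigators report clinically relevant laboratory changes as Protocol 9.2.4 requires.

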10.3.2.3.3 Vital Signs

The analyses of vital signs will include summary statistics at each measurement time point for each treatment group.

10.3.2.3.4 Physical Measurements

The analyses of physical measurements will include summary statistics at each measurement time point for each treatment group.

10.3.2.3.5 Exposure to Investigational Product

The patient-month exposure to investigational product, the categorical representation of dose received, and the total quantity of investigational product used by treatment group will be summarized using descriptive statistics.

12.1 Appendix 1. List of Abbreviations and Definitions of Terms

Abbreviation or Term	Definition/Explanation
ACC	American College of Cardiology
AHA	American Heart Association
AI	autoinjector
ALP	alkaline phosphatase
ALT	alanine aminotransferase
ANA	anti-nuclear antibody
ANCOVA	analysis of covariance
ApoA1	apolipoprotein A1
ApoB	apolipoprotein B
AST	aspartate aminotransferase
BIL	bilirubin
CAD	coronary artery disease
CABG	coronary artery bypass grafting
CANTAB	Cambridge Neuropsychological Text Automated Battery
CBC	complete blood count
CETP	cholesterol ester transfer protein
CFR	Code of Federal Regulations
CI	confidence interval
CIOMS	Council for International Organizations of Medical Sciences
COA	clinical outcome assessment
CPK	creatine phosphokinase
CRF	case report form
CTCAE	Common Terminology Criteria for Adverse Events
CTT	Cholesterol Treatment Trialists'
CYP	cytochrome P450
DILI	drug-induced liver injury
EC	Executive Committee
ECG	electrocardiogram
EDC	electronic data capture
eGFR	estimated glomerular filtration rate
e-mail	electronic mail
Electronic Source Data (eSource)	source data captured initially into a permanent electronic record used for the reconstruction and evaluation of a trial.
End of Follow-up	defined as when the last subject completes the last protocol-specified assessment in the study

Approved

Abbreviation or Term	Definition/Explanation
End of Study (EOS) for Individual Subject	defined as the last day that protocol-specified procedures are conducted for an individual subject
End of Study (EOS) (end of trial)	defined as the date when the last subject is assessed or receives an intervention for evaluation in the study (ie, last subject last visit), following any additional parts in the study (eg, long-term follow-up), as applicable
End of Treatment	defined as the last assessment for the protocol-specified treatment phase of the study for an individual subject
FAS	full analysis set
FCT	fibrous cap thickness
FSH	follicle stimulating hormone
GCP	Good Clinical Practice
HCV	hepatitis C virus
HDL-C	high-density lipoprotein cholesterol
HIPAA	Health Insurance Portability and Accountability Act
HoFH	homozygous familial hypercholesterolemia
HR	hazard ratio
HRT	hormonal replacement therapy
ICH	International Council for Harmonisation
ICMJE	International Committee of Medical Journal Editors
ID	identification
IEC	Independent Ethics Committee
IFU	instructions for use
index date	date subject is admitted to a hospital for a specific condition
INR	international normalized ratio
IPIM	Investigational Product Instruction Manual
IRB	Institutional Review Board
IUD	intrauterine device
IUS	intrauterine hormonal-releasing system
Interactive Voice Response System (IVRS)	telecommunication technology that is linked to a central computer in real time as an interface to collect and process information
IVUS	intravascular ultrasound
Interactive Web Response System (IWRS)	web based technology that is linked to a central computer in real time as an interface to collect and process information
LBBB	left bundle branch block
LDH	lactate dehydrogenase
LDL	low-density lipoprotein
LDL-C	low-density lipoprotein cholesterol

Approved

Abbreviation or Term	Definition/Explanation
LDLR	low-density lipoprotein receptor
LKM1	liver kidney microsomal antibody-1
Lp(a)	lipoprotein(a)
MI	myocardial infarction
NASH	nonalcoholic fatty liver disease including steatohepatitis
NOAEL	no-observed-adverse-effect level
NSTE-ACS	non-ST-segment elevation acute coronary syndrome
NSTEMI	non-ST-segment elevation myocardial infarction
OCT	optical coherence tomography
PAV	percent atheroma volume
PCI	percutaneous coronary intervention
PCSK9	proprotein convertase subtilisin/kexin type 9
POR	Proof of Receipts
Q2W	every 2 weeks
QM	monthly (every 4 weeks with a window of \pm 3 days for each visit or dose)
SAT	Safety Assessment Team
SEC	Self-Evident Corrections
SC	subcutaneous
SD	standard deviation
Source Data	information from an original record or certified copy of the original record containing patient information for use in clinical research. The information may include, but is not limited to, clinical findings, observations, or other activities in a clinical trial necessary for the reconstruction and evaluation of the trial. Source data are contained in source documents (original records or certified copies). (ICH Guideline [E6]). Examples of source data include Subject identification, Randomization identification, and Stratification Value.
SUSAR	suspected unexpected serious adverse reactions
STEMI	ST-segment elevation myocardial infarction
Study Day 1	defined as the first day that protocol-specified investigational product(s)/protocol-required therapies is/are administered to the subject
TAV	total atheroma volume
TC	total cholesterol
TBL	total bilirubin
ULN	upper limit of normal
US	United States
VLDL-C	very low-density lipoprotein cholesterol

Approved

Abbreviation or Term	Definition/Explanation
WHODRUG	World Health Organization Drug

Approved

12.2 Appendix 2. Clinical Laboratory Tests

The tests detailed in [Table 12-1](#) will be performed by the local laboratory, or the central laboratory.

Whenever the local laboratory is used to make either a study treatment decision or response evaluation, the results must be entered into the case report form (CRF).

Protocol-specific requirements for inclusion or exclusion of subjects are detailed in [Section 6.1](#) to [Section 6.2](#) of the protocol.

Additional tests may be performed at any time during the study as determined necessary by the investigator or required by local regulations.

Table 12-1. Analyte Listing

Laboratory: Chemistry	Laboratory: Coagulation	Laboratory: Hematology	Other Labs
Creatinine hs-Troponin (I/T)	-	-	Serum or Urine Pregnancy Lipid Testing 
 • Total cholesterol • HDL-C • LDL-C • Triglycerides • VLDL-C • Non-HDL-C • ApoA1 • ApoB • ApoB/ApoA1 ratio • Total Cholesterol/HDL-C ratio • Lp(a) Biomarkers

Apo = apolipoprotein; HDL-C = high-density lipoprotein cholesterol; hs = high sensitive; LDL-C = low-density lipoprotein cholesterol; Lp(a) = lipoprotein(a); VLDL-C = very low-density lipoprotein cholesterol

Laboratory/analyte results that could unblind the study will not be reported to investigative sites or other blinded personnel until the study has been unblinded. Central laboratory results of the lipid testing will be blinded post-treatment until unblinding of the clinical database and will not be reported to the investigator post-screening. In addition, investigators and staff involved with this trial and all medical staff involved in the subject's medical care should refrain from obtaining lipid panels between randomization and at least 12 weeks after the subject ends the study (to avoid potential unblinding).

Approved

